females) associated with T2D, but not a higher risk for bladder cancer [R15-4869]. Another Swedish inpatient register-based cohort indicated a higher risk of kidney cancer associated with T2D in both women (SIR = 1.7, 95% CI; 1.4-2.0) and men (SIR = 1.3; 95% CI; 1.1-1.6) throughout the duration of follow-up (1-25 years) [R10-6630]. Crude IRs of bladder cancer in patients with T2D range from 38 per 100,000 PY in women from Denmark [R12-1334] to 140-150 per 100,000 PY in men in Sweden and Denmark [R12-0368, R12-1334]. Meta-analyses of observational studies suggest that incidence of kidney cancer in patients with T2D is approximately 40% higher than that in the general population [R13-1812]. The available crude incidence estimates of renal cancer in men with T2D range between 40 and 50 per 100,000 PY in most studies.

Co-existence of hyperinsulinemia and hyperglycaemia in T2D and associated obesity may have a higher associated risk for cancers [R10-6494]. However, there may be additional risks from antidiabetic treatments and insulins, albeit these may be non-significant risks [R10-6494]. Other risk factors of urinary tract cancer are smoking amount and duration [R15-4868], different occupational and environmental exposures [R15-4865], history of kidney/ureter stones [R15-4863], sex, chronic bladder irritation and infections, genetics and family history, chemotherapy and radiation therapy [R15-4866; R15-4856].

6.1.1 Incidence of urinary tract malignancies in the study population in the UK and Sweden observed in the fifth interim report of this study

The country-specific IRs of urinary tract malignancies were estimated in the study population identified in the UK, Sweden and Finland, from 1st August 2014 to 31st December 2020 (2019 for Sweden).

In the UK CPRD GOLD, during a total of 147,020 patient years, 164 urinary tract cancer events were recorded in the study population with an incidence rate of 111.5 (95% CI, 95.7-130.0) per 100,000 patient years. The incidence rate of bladder cancer was 66.7 (95% CI, 54.7-81.2) per 100,000 patient years with a total of 98 events. For renal cancer, the incidence rate was 26.5 (95% CI, 19.4-36.3) per 100,000 patient years with a total of 39 events.

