8.2.4 Baseline and look-back (pre-index) period

To characterise the empagliflozin, or DPP-4 inhibitor cohorts at the time of study drug initiation, all information available during the look-back (pre-index) time period will be collected. The look-back time period is defined as the time period ending on the day before the index date. Since all cohort members are required by inclusion criteria to have at least 1 year of data before the index date (baseline period), the look-back period will include at least 365 days during which covariates can be evaluated. For some study participants, data on covariates might be available beyond 1 year prior to the index date; in these cases, all available information will be considered for covariate classification related to diabetes, diabetes medications, and concomitant chronic conditions. For concomitant medications for diseases other than diabetes, the look-back time period will be limited to 180 days prior to the index date.

If the distribution of the duration of look-back time period is different among empagliflozin, or DPP-4 inhibitor categories of look-back time will be created using indicator variables. Those indicator variables will then be used as covariates in the multivariable regression models for outcome prediction, and for PS development, to control for possible differences in availability of information between the empagliflozin and comparator cohorts.

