8.4 DATA SOURCES

Prior to the development of the protocol for this study, a feasibility assessment of three databases in Europe (CPRD [GOLD and Aurum] and data with potential for linkage [HES (Outpatient and Admitted Patient Care), and ONS mortality statistics] in the UK and the national registers in Sweden and Finland) was performed with the aim to detail the minimum data requirements for the study and to assess, for each potential data source, the data quality, completeness of recorded information for urinary tract malignancies, and possibility of linkage with cancer registries, mortality registries and other data sources. The minimal data requirements for data sources which were assessed are listed in [Table 5](#).

Table 5

Minimum data requirements and data availability for the UK and the national registries in Sweden and Finland.

	The UK				Sweden					Finland						
	CPRD (GOLD and Aurum)	HES	Mortal ity		Patient	Prescri ption	Cancer	Cause of	Diabet es	HILM O	AvohI LMO	Special Reimb	Prescip tions	Cause of	Cancer s	EMR databa
Age	X	X	X	X	X	X	X	X	X	X	X	-	X	X	X	
Sex	X	X	X	X	X	X	X	X	X	X	X	-	X	X	X	
Medication	X	-		X ³	X	-	-	X ⁵	-	-	-	-	X	-	X	
DDD	X	-	-	X	X	-	-	-	-	-	-	-	X	-	-	
Purchase date	X ¹	-	-	X	X	-	-	-	-	-	-	-	X	-	-	
Diagnoses	X	X	-	X ⁴	-	X	-	X	X	X	X ⁷	X ⁹	-	X	-	
Date of diagnosis	X	X	-	X	-	X	-	-	X	X	X ⁸	-	-	X	-	
Time of death	-	-	X	-	-	X	X	-	-	-	-	-	-	X	X	
Cause of death	-	-	X	-	-	X	X	-	-	-	-	-	-	X	X	
Smoking	X	-	-	-	-	-	-	X	X ⁶	X ⁶	-	-	-	-	X	
BMI	X	-	-	-	-	-	-	X	X ⁶	X ⁶	-	-	-	-	X	
HbA1c	X	-	-	-	-	-	-	X	-	-	-	-	-	-	X	

X = available in the register, - = not available in the register

1 Prescription date; 2 Month and year; 3 Treatment given in hospitals (no full coverage); 4 No primary care data; 5 Only type of medication; 6 Partial availability based on applicable diagnosis codes; 7 Only chronic diseases included in the special reimbursement scheme; 8 Start and end dates of the special reimbursement; 9 In case a special reimbursement was included in the purchase

AvoHILMO=Register of primary health care visits, BMI=body mass index, CPRD=Clinical Practice Research Datalink, DDD=Defined daily dose, EMR=electronic medical record, HbA1c=Glycated haemoglobin A1c, HES=Hospital Episode Statistics (Outpatient data, and Admitted Patient Care data), HILMO=Care register for health care; UK =The United Kingdom

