Estimated glomerular filtration rate (eGFR) at index date	
eGFR estimate derived from serum creatinine measurement using the CKD-Epi equation:
 $\text{eGFR (mL/min/1.73 m}^2\text{)} = 141 \times \min(\text{S}_{\text{cr}}/\text{K}, 1)^a \times \max(\text{S}_{\text{cr}}/\text{K}, 1)^{-1.209} \times 0.993^{\text{Age}} \times 1.018 \text{ [if female].}$ 
a = -0.329 (females) or -0.411 (males).
 
Evaluated at index using closest value to index date.
	
Time-fixed Continuous Categorical <15 (ml/min/1.73 m²) (kidney failure) 15-29 (ml/min/1.73 m²) (severely decreased) 30-44 (ml/min/1.73 m²) (Moderately to severely decreased) 45-59 (ml/min/1.73 m²) (Mildly to moderately decreased) 60-89 (ml/min/1.73 m²) (Mildly decreased) ≥90 (ml/min/1.73 m²) (Normal)
	
UK: CPRD Sweden: NDR Finland: EMR databases

Proprietary confidential information © 2024 Boehringer Ingelheim International GmbH or one or more of its affiliated companies

Renal impairment at index date	
The variable is evaluated at index date and indicates an eGFR < 60 (ml/min/1.73 m²) in all available history prior to index date.
 
Evaluated at index date using all available history prior to index date.
	
Time-fixed Categorical Yes No
	
UK: CPRD Sweden: NDR Finland: EMR databases

UTI or pyelonephritis	
The variable is initialized at index date and indicates a register record with a diagnosis of UTI or pyelonephritis using all available history. If no diagnosis prior to index date, it is time-updated to indicate any diagnosis of UTI or pyelonephritis after index date.
 
ICD-10 and READ diagnosis codes for UTI or pyelonephritis in Annex I.
 
Initialized at index and updating from index date onwards.
	
Time-dependent Categorical: Yes No
	
UK: CPRD Sweden: NPR Finland: HILMO, AvoHILMO

Liver disease at index date	
The variable is evaluated at index date and indicates a register record with a diagnosis of liver disease using all available history prior to index date.
 
ICD-10 and READ diagnosis codes for liver disease in Annex I.
 
Evaluated at index date using all available history prior to index date.
	
Time-fixed Categorical: Yes No
	
UK: CPRD Sweden: NPR Finland: HILMO, AvoHILMO

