Statins, fibrates exposure at index date	Exposure status at index date of any statin or fibrate (including combinations) based on purchased amounts and daily defined dose using data within 180-day period prior to index date. ATC codes for statins, fibrates in Annex II. Evaluated at index date using data within 180-day period prior to index date.	Time-fixed Categorical: Yes No	UK: CPRD Sweden: SPDR Finland: FPR

Proprietary confidential information © 2024 Boehringer Ingelheim International GmbH or one or more of its affiliated companies

Lipid modifying agents exposure at index date	Exposure status at index date of any lipid-modifying agent (including combinations) based on purchased amounts and daily defined dose using data within 180-day period prior to index date.	Time-fixed Categorical: Yes No	UK: CPRD Sweden: SPDR Finland: FPR
ATC codes for lipid modifying agent in Annex II.			
Evaluated at index date using data within 180-day period prior to index date.			
Zoledronic acid exposure at index date	Exposure status at index date of any zoledronic acid (including combinations) based on purchased amounts and daily defined dose using data within 180-day period prior to index date.	Time-fixed Categorical: Yes No	UK: CPRD Sweden: SPDR Finland: FPR
ATC codes for zoledronic acid in Annex II.			
Evaluated at index date using data within 180-day period prior to index date.			
Antibiotics exposure at index date	Exposure status at index date of any antibiotic (including combinations) based on purchased amounts, daily defined dose and dose per time estimation using data within 180-day period prior to index date.	Time-fixed Categorical: Yes No	UK: CPRD Sweden: SPDR Finland: FPR
ATC codes for antibiotic in Annex II.			
Evaluated at index date using data within 180-day period prior to index date.			

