Proprietary confidential information © 2024 Boehringer Ingelheim International GmbH or one or more of its affiliated companies

	Empagliflozin at index date	DPP-4 inhibitors at index date	[Country] Study population (Total)
	N	N	
Yes	N (x.xx%)	N (x.xx%)	N (x.xx%)
No	N (x.xx%)	N (x.xx%)	N (x.xx%)
History of congestive heart failure prior to index date			
Yes	N (x.xx%)	N (x.xx%)	N (x.xx%)
No	N (x.xx%)	N (x.xx%)	N (x.xx%)
History of hypertension prior to index date			
Yes	N (x.xx%)	N (x.xx%)	N (x.xx%)
No	N (x.xx%)	N (x.xx%)	N (x.xx%)
History of stroke prior to index date			
Yes	N (x.xx%)	N (x.xx%)	N (x.xx%)
No	N (x.xx%)	N (x.xx%)	N (x.xx%)
History of myocardial infarction prior to index date			
Yes	N (x.xx%)	N (x.xx%)	N (x.xx%)
No	N (x.xx%)	N (x.xx%)	N (x.xx%)
History of autoimmune disease prior to index date			
Yes	N (x.xx%)	N (x.xx%)	N (x.xx%)
No	N (x.xx%)	N (x.xx%)	N (x.xx%)
History of COPD prior to index date			
Yes	N (x.xx%)	N (x.xx%)	N (x.xx%)

Proprietary confidential information © 2024 Boehringer Ingelheim International GmbH or one or more of its affiliated companies

	Empagliflozin at index date	DPP-4 inhibitors at index date	[Country] Study population (Total)
	N	N	
No	N (x.xx%)	N (x.xx%)	N (x.xx%)
Any ICU admission prior to index date			
Yes	N (x.xx%)	N (x.xx%)	N (x.xx%)
No	N (x.xx%)	N (x.xx%)	N (x.xx%)
Antihypertensives/ diuretics use prior to index date			
Yes	N (x.xx%)	N (x.xx%)	N (x.xx%)
No	N (x.xx%)	N (x.xx%)	N (x.xx%)
NSAIDs use prior to index date			
Yes	N (x.xx%)	N (x.xx%)	N (x.xx%)
No	N (x.xx%)	N (x.xx%)	N (x.xx%)
Oral steroids use prior to index date			
Yes	N (x.xx%)	N (x.xx%)	N (x.xx%)
No	N (x.xx%)	N (x.xx%)	N (x.xx%)
Statins/fibrates use prior to index date			
Yes	N (x.xx%)	N (x.xx%)	N (x.xx%)
No	N (x.xx%)	N (x.xx%)	N (x.xx%)
Lipid modifying agents use prior to index date			
Yes	N (x.xx%)	N (x.xx%)	N (x.xx%)

Proprietary confidential information © 2024 Boehringer Ingelheim International GmbH or one or more of its affiliated companies

	Empagliflozin at index date	DPP-4 inhibitors at index date	[Country] Study population (Total)
	N	N	
No	N (x.xx%)	N (x.xx%)	N (x.xx%)
Zoledronic acid use prior to index date			
Yes	N (x.xx%)	N (x.xx%)	N (x.xx%)
No	N (x.xx%)	N (x.xx%)	N (x.xx%)
Antibiotic use prior to index date			
Yes	N (x.xx%)	N (x.xx%)	N (x.xx%)
No	N (x.xx%)	N (x.xx%)	N (x.xx%)
BMI (closest value prior to index date)			
<20	N (x.xx%)	N (x.xx%)	N (x.xx%)
20-24.9	N (x.xx%)	N (x.xx%)	N (x.xx%)
25-29.9	N (x.xx%)	N (x.xx%)	N (x.xx%)

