Yes	N (x.xx%)	N (x.xx%)	χ^2 test p-value	std diff
No	N (x.xx%)	N (x.xx%)		
Zoledronic acid use at index date				
Yes	N (x.xx%)	N (x.xx%)	χ^2 test p-value	std diff
No	N (x.xx%)	N (x.xx%)		

Proprietary confidential information © 2024 Boehringer Ingelheim International GmbH or one or more of its affiliated companies

	Empagliflozin users at index date [before/after] matching	DPP-4 inhibitors users at index date [before/after] matching	P-Value	Standardized differences
	N	N		
Antibiotic use at index date				
Yes	N (x.xx%)	N (x.xx%)	χ^2 test p-value	std diff
No	N (x.xx%)	N (x.xx%)		
BMI (closest value prior to index date)				
<20	N (x.xx%)	N (x.xx%)	χ^2 test p-value	std diff
20-24.9	N (x.xx%)	N (x.xx%)	χ^2 test p-value	std diff
25-29.9	N (x.xx%)	N (x.xx%)	χ^2 test p-value	std diff
>30	N (x.xx%)	N (x.xx%)	χ^2 test p-value	std diff
Range (min,max)	(min, max)	(min, max)		
mean (\pm sd)	mean (\pm sd)	mean (\pm sd)	t-test p-value	std diff
median (Q1,Q3)	median (Q1,Q3)	median (Q1,Q3)		
Smoking status (closest value prior to index date)				
Yes	N (x.xx%)	N (x.xx%)	χ^2 test p-value	std diff
No	N (x.xx%)	N (x.xx%)		
Alcohol use (closest value prior to index date)				
Yes	N (x.xx%)	N (x.xx%)	χ^2 test p-value	std diff
No	N (x.xx%)	N (x.xx%)		

Proprietary confidential information © 2024 Boehringer Ingelheim International GmbH or one or more of its affiliated companies

	Empagliflozin users at index date [before/after] matching	DPP-4 inhibitors users at index date [before/after] matching	P-Value	Standardized differences
	N	N		
HbA1c mmol/mol (closest value prior to index date)				
< 48 (6.5%) mmol/mol	N (x.xx%)	N (x.xx%)	χ^2 test p-value	std diff
\geq 48 (6.5 %) - <64 mol/mol (8 %)	N (x.xx%)	N (x.xx%)	χ^2 test p-value	std diff
\geq 64 mmol/mol (8 %)	N (x.xx%)	N (x.xx%)	χ^2 test p-value	std diff
Range (min,max)	(min, max)	(min, max)		
mean (\pm sd)	mean (\pm sd)	mean (\pm sd)	t-test p-value	std diff
median (Q1,Q3)	median (Q1,Q3)	median (Q1,Q3)		
Number of albuminuria tests at index date				
Range (min,max)	(min, max)	(min, max)		
mean (\pm sd)	mean (\pm sd)	mean (\pm sd)	t-test p-value	std diff
median (Q1,Q3)	median (Q1,Q3)	median (Q1,Q3)		
eGFR in (mL/min/1.73 m²)				
<15 (ml/min/1.73 m ²) (kidney failure)	N (x.xx%)	N (x.xx%)	N (x.xx%)	N (x.xx%)
15-29 (ml/min/1.73 m ²) (severely decreased)	N (x.xx%)	N (x.xx%)	N (x.xx%)	N (x.xx%)
30-44 (ml/min/1.73 m ²) (Moderately to severely decreased)	N (x.xx%)	N (x.xx%)	N (x.xx%)	N (x.xx%)

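### SAP Table 15 reads as index-day supply status for antibiotics and other short-course drugs, conflicts with the labels in Tables 17 and 37, and would miss most users in the 180-day look-back

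*SAP*

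**What the plan says.** SAP Section 5.3.3, Table 15, gives all non-diabetes drugs one form of definition: exposure status at the index date, derived from purchased amounts and defined daily dose. The antibiotic row reads "Exposure status at index date of any antibiotic (including combinations) based on purchased amounts, daily defined dose and dose per time estimation". The timing line for these rows is "Evaluated at index date using data within 180-day period prior to index date". Protocol 8.2.4 sets the window: "For concomitant medications for diseases other than diabetes, the look-back time period will be limited to 180 days prior to the index date".

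The shells in SAP Annex III label the variable differently. Table 17 (baseline description) has "Antibiotic use prior to index date", and Table 37 does the same for the two CPRD databases. Table 18 (covariate balance) has "Antibiotic use at index date". Tables 22 and 38 give no timing.

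SAP 6.5.1 and 6.6.2 send the Table 15 variables to the propensity score and the balance check. Under SAP 6.6.2 and 6.7.2, a propensity score covariate enters the base Cox model only if its standardized difference after matching is 10% or more.

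The related disease covariate in SAP Table 13 "indicates a register record with a diagnosis of UTI or pyelonephritis using all available history". Its Swedish source is the National Patient Register alone. Protocol Table 5 annotates that register's diagnoses "4 No primary care data".

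**The concern.** A supply-based status on one day suits drugs taken continuously. For a drug taken for a week or two, it records only patients who happen to be in mid-course on the index day. Anyone whose course ended earlier in the 180 days is coded No, and the look-back loses most of its purpose.

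Antibiotics are where this matters. Protocol 6.1 lists "chronic bladder irritation and infections" among the risk factors for urinary tract cancer. Among the covariates listed for Sweden, antibiotic dispensing is the only one likely to reflect infections treated in primary care. Sweden is expected to supply 32,334 of 67,490 empagliflozin initiators (Protocol Table 6), or 48%. If the covariate is nearly empty in both groups, a moderate difference in recent antibiotic use shrinks below the 10% rule, and neither matching nor the base model does much about it.

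The conflicting labels are a second problem. Two programmers could derive different variables, and the baseline table could show an imbalance that the balance table does not.

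**Working it through.** **Which reading the text favours.** Purchased amounts and defined daily dose are needed only to work out how long a supply lasts; a flag for any dispensing needs neither. SAP 5.1.4 gives a days'-supply rule for non-study drugs. SAP Table 14 keeps the two ideas apart: its current metformin exposure variable is built from amounts and daily dose, while its ever-exposed variables record any use. Table 15 follows the first form. Table 17 has separate rows for insulin use before and at index, so the SAP treats these as different variables.

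**Share of users coded No.** The documents give no misclassification figure to reproduce, no course length and no grace period for these drugs. All of the following are therefore assumptions: one course of L days' supply, dispensed uniformly over 180 days, and a grace period g of 0 or 30 days (30 days is the rule for study drugs in SAP 5.1.6). Share coded No = 1 − (L + g)/180.

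| Days' supply | g = 0 | g = 30 |
|---|---|---|
| 7 | 96.1% | 79.4% |
| 10 | 94.4% | 77.8% |
| 14 | 92.2% | 75.6% |
| 30 | 83.3% | 66.7% |
| 90 | 50.0% | 33.3% |

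With two independent courses and no grace period, (1 − L/180)² gives 92.4% at 7 days and 85.0% at 14 days.

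**Effect on the balance check.** SAP 6.6.2 defines d = 100 × (p1 − p2) / √{[p1(1 − p1) + p2(1 − p2)]/2}. Assume any use in 180 days of 30% vs 24%:

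- Any-use definition: 6 / √[(0.2100 + 0.1824)/2] = 6 / 0.443 = 13.5%, above the 10% rule.
- 7 days, g = 0: prevalences × 7/180 = 1.17% vs 0.93%, d = 2.3%.
- 10 days, g = 0: 1.67% vs 1.33%, d = 2.7%.
- 14 days, g = 0: 2.33% vs 1.87%, d = 3.3%.
- g = 30: × 37/180 gives 6.2% vs 4.9%, d = 5.4% (7 days); × 44/180 gives 7.3% vs 5.9%, d = 5.9% (14 days).

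Larger assumed imbalances, g = 0:

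| Any use | d, any use | d, 7 days | d, 14 days |
|---|---|---|---|
| 30% vs 20% | 23.2% | 4.0% | 5.6% |
| 40% vs 20% | 44.7% | 7.2% | 10.3% |
| 50% vs 20% | 66.3% | 10.1% | 14.4% |

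**Would the p-value show it?** Take Sweden at 32,334 per group with 1:1 matching. For 30% vs 24% as coded at 7 days, SE = √(2 × 0.01039/32,334) = 0.00080. The difference of 0.00233 is then z = 2.91, and power at the two-sided 5% level is about 83%. At 14 days it is about 98%. The chi-square test would often flag the gap, but the p-value does not decide entry to the base model.

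**The case against.** The strongest reply is that Table 15 never says supply must cover the index day. Elsewhere the SAP uses the phrase loosely: intensive care admission, stroke and COPD are all named as at index date but mean any record in prior history, and Section 6.5.1 applies the same phrase to those tables. Tables 17 and 37 and the 180-day look-back fit an any-use intention. This stands to the extent that the authors' intent is not settled. A reader might infer that the SAP certainly codes index-day supply; the documents support only that this is the more literal reading, and that the labels conflict.

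A reader might also infer that 92–96% applies to NSAIDs and oral steroids as well. It does not: longer or repeated supply lowers it, to 83% at 30 days and 50% at 90 days. Protocol 6.1 does not name either drug class as a risk factor.

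A third tempting inference is that an imbalance cannot show at all. The working contradicts it: 40% vs 20% reaches 10.3% with 14-day courses, and p-values are reported alongside.

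Finally, the infection covariate limits the damage. It uses all history, is a time-updated candidate for the adjusted model regardless of the balance check, and draws on GP data in the UK and on HILMO and AvoHILMO (primary care visits) in Finland. The antibiotic variable covers all systemic antibacterials and is at best a proxy for urinary infection. These points narrow the concern mainly to antibiotics in Sweden; they do not remove it.

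**Conclusion.** The point holds as an unclear and internally inconsistent definition whose literal reading works badly for short-course drugs. On that reading, and assuming a single course, uniform timing and no grace period, 92–96% of users with 7–14 days' supply are coded No. With a 30-day grace period it is 76–79%.

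A moderate imbalance is strongly attenuated: an assumed 13.5% appears as 2–3%, or 5–6% with the grace period. It then passes the 10% rule and stays out of the base model. The propensity score, which receives the same variable, controls it poorly.

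The course lengths and prevalences are assumptions. The documents do not show that antibiotic use differs between the groups, and no effect on the hazard ratio has been estimated, so a reader should not infer a bias of known size. It should be corrected because the change is almost free and Sweden has no primary care substitute.

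**What to change.** In SAP Table 15, define antibiotics as Yes if there is at least one dispensing or prescription in days −180 to −1 before index. Apply the same rule to oral steroids and NSAIDs, where use is short or as needed. Use that definition in the propensity score and in the balance check. If index-day supply status is kept for the long-term drugs in the table, say so and state any grace period. Align the labels in Tables 15, 17, 18, 22, 37 and 38.

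The cost is SAP wording and a simpler derivation on data already being extracted. The rule fits the 180-day look-back in Protocol 8.2.4, so the protocol text on this point need not change.

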6. PLANNED ANALYSIS

6.1. SUMMARY OF STUDY POPULATION IDENTIFICATION

The identification process used to identify the study populations and subgroups will be summarised using population flowcharts including the following information:

- The total number of patients in the source population.
- The number and proportion of patients not meeting inclusion criteria.
- The number and proportion of patients meeting inclusion criteria.
- The number and proportion of patients excluded after applying exclusion criteria.

Proprietary confidential information © 2024 Boehringer Ingelheim International GmbH or one or more of its affiliated companies

- The number and proportion of patients included in the study after applying inclusion and exclusion criteria [total study population].
- The number and proportion of patients using empagliflozin (out of total study population) at index date.
- The number and proportion of patients using DPP-4 inhibitors (out of total study population) at index date.

For each of the study countries, a population flowchart similar to Figure 2 will be presented.

